The results from two Phase III studies in myelofibrosis (COMFORT-I, COMFORT-II) demonstrate the effectiveness of ruxolitinib in patients with PMF, PPV-MF and PET-MF. The results of these two studies were consistent, demonstrating statistically significant ($p < 0.0001$) differences in rates of $\geq 35\%$ spleen volume reduction compared with either placebo or an investigator's selection of best available therapy (BAT). Although, the time point for the

primary endpoint (spleen volume reductions) were different in COMFORT-I (at Week 24) and COMFORT-II (at Week 28) the mean reduction in spleen volume is similar at Week 24 (31.6% vs. 29.2%, COMFORT-I and COMFORT-II, respectively).

The COMFORT-I trial is a randomized, double-blind, placebo-controlled Phase III study of the oral JAK1/JAK2 inhibitor INC424 in 309 patients with PMF, PPV MF, or PET-MF. Patients from 89 sites in the USA, Canada and Australia were randomized 1:1 to receive either INC424 (15 mg PO BID or 20 mg PO BID depending on baseline platelet count) or placebo. The primary endpoint of the study was the proportion of patients achieving $\geq 35\%$ reduction in spleen volume from baseline to Week 24 as measured by MRI (or CT scan in applicable patients) and the secondary endpoints included: duration of maintenance of a $\geq 35\%$ reduction from baseline in spleen volume among patients initially randomized to receive INC424, and the proportion of patients with $\geq 50\%$ reduction in total symptom score from baseline to Week 24 as measured by the modified MFSAF v2.0 diary.

A total of 309 patients were enrolled in the study, with 155 randomized to INC424 and 154 to placebo. The groups were matched for baseline characteristics; the majority of patients had high-risk disease (61.2%). Patients were eligible to cross-over in this study, and 36 patients in the placebo group (23.4%) crossed over to INC424. The data cutoff date was 2-Nov-2010, the date of last patient last visit.

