2.3 Assessment windows, baseline and post baseline definitions, missing data handling

Assessment windows:

On-treatment, evaluations are scheduled for study visits at Day 1, and at the end of Weeks 4, 8, 12, and every 12 weeks thereafter with time window of +/- 7 days.

Baseline definition:

Baseline is the latest available assessment obtained prior to the date of first dose of study drug administration. If assessment prior to first dose of study drug administration is not available, then assessment on the day of first dose of study drug administration will be used at baseline. Otherwise baseline will be considered missing.

Post baseline definition:

All assessments obtained after the baseline assessment (see definition above) are considered as post-baseline.

Study day calculation:

In this study, we will use study day instead of actual event date.

Study day will be calculated as

- event date - start date of study drug + 1, if the event date is on or after the start date of study drug or
- event date - start date of study drug, if the event date is prior to the start date of study drug

Month for this study will be considered as 4 weeks, so that Month 1 is at Week 4 and so on.

Similarly, quarter would be considered as 12 weeks, so that Quarter 1 is at Week 12 and so on.

Data Handling:

All patients will be followed-up for 28 days after they have discontinued INC424, data collected during this follow-up period will be included in the analysis.

Unless otherwise specified, no imputation for missing data will be performed.

3 Statistical analysis

This section describes the planned statistical analyses for Sections 10-12, 14, and 16 of the clinical study report.

The final analysis for this study will be performed after all patients have either completed or have been prematurely discontinued from the study.

Unless otherwise specified, qualitative data (e.g., gender) will be described using frequency and percentages, while quantitative data, will be described using descriptive statistics: n, mean, standard deviation, median, minimum, and maximum.

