3.4.3 Analysis of secondary endpoints

In this section the term 'percent of change from baseline' at a time T is defined as per following definition:

$$\% \text{ change at time T} = \frac{\text{Week T value} - \text{Baseline value}}{\text{Baseline value}} \times 100$$

At least 50% reduction in spleen length from baseline at any time: The proportion of patients who achieved at least 50% reduction in spleen length at any time will be displayed along with the 95% CI for proportion of reduction.

If a patient is palpable at Baseline and becomes non-palpable at post-baseline, then this post-baseline value will be imputed as 0 (zero).

The proportion of responders (achieving at least 50% reduction in spleen length at any time from baseline) will be estimated for patients whose spleen were palpable at baseline and remained palpable or became non palpable at the post-baseline visit. In addition to the FAS, this analysis will also be done by the PPS.

Time to response is defined as the time between date of start of treatment to the date of first response. Response is defined by the 50% reduction in spleen length from baseline. Summary statistics for those responders will be provided.

Duration of response is defined as the time between date of first response ($\geq 50\%$ reduction in spleen length from baseline) to date of loss of response or death due to MF. Loss of response is defined as going back to baseline level after first time $\geq 50\%$ reduction in spleen length from baseline. In case a patient does not have loss of response or death due to myelofibrosis by the data cutoff date, DOR will be censored at the date of the last adequate assessment of spleen length OR cut-off date whichever occurs first.

Best overall response to treatment as assessed by spleen palpation is defined by the investigator.

Best overall response is defined as the best response observed during the study follow-up period. The proportion of patients in the best overall response category will be summarized.

In addition, best overall response will be evaluated and summarized by the IWG MRT criteria given in Section 3.11.2.

Change of spleen length from Baseline to end of each visit/month of therapy and at end of treatment. The change in spleen length from Baseline to end of each visit/month of therapy and at end of treatment will be described using descriptive statistics and by relevant change categories:

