3.11 Other topics

3.11.1 Handling of missing data

Patients with missing baseline values where a change from baseline is calculated or when the baseline is used as a covariate will be excluded from the analysis of that variable. Missing values in the QoL will be handled following the instruction of the instruments.

[figure not shown]
3.11.2 Table of Spleen Response and Loss of Response Criteria by IWG MRT criteria

Patients with spleen length at baseline	Response criteria	Loss of response criteria 1
Less than 5 cm	Non evaluable for response	Non evaluable for loss of response
Between 5 and 10 cm	Responder: achieve non palpable spleen	Splenomegaly 5 cm or more
	Stable disease: does not meet criteria for response NOR for disease progression	Meet criteria of progressive disease
	Progressive disease: increase of 100% from baseline	-
More than 10 cm	Responder: reduction of 50%	Loss of the 50% reduction
	Stable disease: does not meet criteria for response NOR for	Meet criteria of progressive disease

[figure not shown]
	disease progression	
	Progressive disease: increase of 50% from baseline	-

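### Duration of spleen response starts at a 50% reduction but ends only at return to baseline length or death due to MF, so time after the 50% reduction is lost counts as response

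*SAP*

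**What the plan says.** SAP 3.4.3 defines response, for time to response and for DOR, as a 50% reduction in palpable spleen length from baseline. DOR runs from the first such reading "to date of loss of response or death due to MF". Loss is then defined: "Loss of response is defined as going back to baseline level after first time" the 50% reduction is seen. Without either event, "DOR will be censored at the date of the last adequate assessment of spleen length" or at the cut-off date, whichever comes first. Deaths not attributed to MF are therefore not events.

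The table in SAP 3.11.2 has a different exit rule. For baseline spleens above 10 cm the entry rule is the same 50% ("Responder: reduction of 50" per cent), and response ends at "Loss of the 50% reduction". The SAP invokes that table for one purpose: "best overall response will be evaluated and summarized by the IWG MRT criteria given in Section 3.11.2". The DOR paragraph does not cite it.

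The protocol's efficacy endpoints (3.3.2 and 11.6.1.1) do not include DOR, so no protocol definition takes precedence. SAP section 4 lists only the transfusion definitions as changes from the protocol. SAP 3.4.3 names Kaplan-Meier for PFS, LFS and OS, and SAP 3.4.4 names it for time to first improvement. No estimator is named for DOR.

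**The concern.** A patient enters at a 50% reduction and leaves at no reduction. Between those two levels nothing stops the clock, although the patient no longer meets the SAP's own definition of response. Slow or partial regrowth then becomes either a much later event or a censored observation. Partial regrowth is not exotic here: Protocol 6.2.1.1.2 itself treats a 2 cm increase over the on-study nadir as noteworthy.

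What is at stake is the meaning of one reported figure. With no comparator and no test, the definition is the whole content of that figure, and most readers will take *duration of response* to mean the time for which the response criterion was held.

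**Working it through.** There is no planned figure to reproduce: the documents give no expected duration, sample size or power. The check is of the definition, followed by illustrations.

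**1. One assumed patient on the SAP schedule.** SAP 2.3 places visits "at the end of Weeks 4, 8, 12, and every 12 weeks thereafter with time window of +/- 7 days". Baseline is 20 cm.

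| Week | 12 | 24 | 36 | 48 | 60 | 72 | 84 | 96 |
|---|---|---|---|---|---|---|---|---|
| Length, cm | 9 | 9 | 12 | 15 | 17 | 19 | 19 | 19 |
| Change, % | -55 | -55 | -40 | -25 | -15 | -5 | -5 | -5 |

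- Ending at loss of the 50% reduction (week 36, confirmed at week 48): 36 - 12 = 24 weeks, an event.
- SAP rule, with week 96 as the last assessment: 96 - 12 = 84 weeks, censored as still responding, although 6 of 8 visits show less than a 50% reduction. The SAP's by-visit table would put the last three visits in its -25% to -5% category.

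**2. Ordering within a patient.** Let w be the visit at which the 50% reduction is first seen to be lost, without confirmation. A spleen back at baseline length has necessarily lost the 50% reduction, so under the same censoring the SAP duration is never shorter than the time to w.

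- It is longer if baseline length was not reached at w and a later spleen assessment exists.
- If w is the last assessment (and no MF death follows), both durations end on the same date. Only the status changes, from event to censored.

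**3. How much time can be added.** Protocol 4.1 gives recruitment to 31 December 2014 and last patient last visit in December 2016, so about 104 weeks for the last enrolled. The spleen is also palpated at End of Treatment (Protocol 7.6.2.1) and at the follow-up visit 28 to 37 days later (7.6.3.1), that is, 104 + 4 to 5.3, or about week 109. With first response at week 12, maximum extra time = last palpation - w.

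| w | Time to loss of 50% (w - 12) | Extra, last palpation week 104 | Extra, last palpation week 109 |
|---|---|---|---|
| 36 | 24 | 68 | 73 |
| 60 | 48 | 44 | 49 |
| 84 | 72 | 20 | 25 |

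The minimum extra time is zero in every row.

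**4. The summary need not move the same way.** Patient A loses the 50% reduction at month 1 and reaches baseline at month 3; B is censored at month 2; C dies of MF at month 5. Ending at loss of 50%: S = 2/3 after month 1 and 0 after month 5, median 5. SAP rule: B leaves the risk set first, S = 1/2 after month 3, median 3. The longer individual duration gives the shorter median.

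**5. What a tighter rule costs in palpation noise.** Assume a measurement SD of 1 cm, independent errors, an error-free baseline B cm, and a truly stable responder at fraction f of baseline. Response at week 12 leaves 7 later 12-weekly readings to week 96. The chance that one reading falls on the wrong side is p = 1 - Φ((0.5 - f)B). With q = 1 - p, the chance of no declared loss (no two consecutive wrong readings and the last one right) follows a(0) = 1, a(1) = q, a(k) = q[a(k-1) + p·a(k-2)]; false loss is 1 - a(7).

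| B, cm | f | p | False loss |
|---|---|---|---|
| 5 | 0.45 | 0.401 | 70% |
| 5 | 0.40 | 0.309 | 55% |
| 16 | 0.45 | 0.212 | 36% |
| 16 | 0.40 | 0.055 | 7% |
| 10 | 0.25 | 0.006 | 0.6% |

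Without confirmation, 1 - (1 - p)^7 at B = 16 is 81% for f = 0.45 and 33% for f = 0.40.

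**The case against.** **The rule is explicit and may be deliberate.** Palpation is noisy, and a wide gap between entry and exit avoids calling a loss on a 1 cm wobble. This has force. Under the assumptions above, even a confirmed 50% rule misclassifies more than half of stable borderline responders with a 5 cm spleen. It is a reason to require confirmation and to keep the return-to-baseline analysis alongside. It does not make time at, say, a 5% reduction time in response.

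**The reader can see the pattern elsewhere.** The by-visit categories show the share at a reduction of 50% or more at each visit, and Protocol section 11 promises individual listings. That stands, and it limits the harm. DOR is also neither a stated objective nor a protocol endpoint.

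**Stronger readings that the documents do not support:**

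- *The reported DOR will be overstated.* This is expected but not certain. The ordering in step 2 is within a patient and against the first unconfirmed loss. A Kaplan-Meier median can move the other way (step 4), and against the confirmed rule an isolated baseline-level reading could reverse the order.
- *The SAP contradicts itself.* Table 3.11.2 is cited only for best overall response. It shows that the SAP knows the tighter exit rule for the same threshold, but it is a separate criterion.
- *Week 96 caps the extra time.* It does not, because End of Treatment and follow-up palpations come later.
- *The figure would otherwise be comparable with the earlier placebo-controlled trial.* Protocol 1.3.5 describes that trial's endpoint ("and the secondary endpoints included: duration of maintenance of a" reduction of at least 35%) in terms of imaged spleen volume. Modality and threshold differ whatever loss rule is used here.
- *The earlier trials' durability figures give the size.* The protocol reports 67% of responders maintaining a reduction for at least 48 weeks in one trial, and 80% still responding at a median follow-up of 12 months in the other. Both concern spleen volume and say nothing about how far palpable length regrows.

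**Conclusion.** The definition does not measure what its name says, and it should be changed. Entry is at 50% and exit at zero, no other section corrects this, and partial regrowers are carried as ongoing responders. The reading of the text is secure.

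The size is not known. The figures of about 68, 44 and 20 weeks (73, 49 and 25 with the follow-up palpation) are maxima for one illustrative case. They assume a last-enrolled patient, first response at week 12 and treatment to about week 104. Other patients may be followed for longer, or for less time where commercial availability ends treatment early. The false-loss figures rest on an assumed 1 cm SD that does not come from the documents.

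Consequences are limited to one descriptive endpoint. No hypothesis test or error rate is involved.

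**What to change.** In SAP 3.4.3:

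- Define loss of response for DOR as the first post-response assessment with a reduction from baseline below 50%, confirmed at the next assessment or with no later assessment available. Date it at the first such reading.
- Keep the current rule as a supportive analysis labelled *time to return to baseline length*.
- State that DOR is estimated by Kaplan-Meier.

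Do not import the 3.11.2 table wholesale. It makes spleens under 5 cm non-evaluable and requires a non-palpable spleen for response between 5 and 10 cm, which would change who counts as a responder.

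The cost is a few lines of SAP text, one recoded endpoint and one supportive run, all from spleen lengths already collected. The likely price is a shorter reported duration and some sensitivity to palpation error, largest for small baseline spleens and borderline responses. That is why both versions should be reported.

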Significantly more patients in the INC424 group had a reduction in spleen volume ($\geq 35\%$) at week 24 (41.9% vs. 0.7%; $P < .0001$). A reduction in spleen volume for ≥ 48 weeks was maintained in 67% patients who achieved a response on INC424. More patients receiving INC424 had an improvement of $\geq 50\%$ in the total symptom score at 24 weeks compared to placebo (45.9% vs. 5.3%, $P < 0.001$). Patient's receiving INC424 also had improvements in each symptom assessed on the MF-SAF. Overall survival was a secondary endpoint of COMFORT-I. Ten deaths occurred in the INC424 group vs. 14 deaths in the placebo group (hazard ratio, 0.67; 95% CI, 0.30 to 1.50; $P = 0.33$). A survival analysis based on a planned data cutoff with 4 additional months of follow-up (median follow-up, 51 weeks) revealed a significant survival advantage for patients who received INC424 (13 deaths in the INC424 group (8.4%) vs. 24 deaths in the placebo group (15.6%) (Hazard ratio, 0.50; 95% confidence interval, 0.25 to 0.98; $P = 0.04$).

INC424 was well tolerated in COMFORT-I, with most Grade 3/4 nonhematologic toxicities occurring in less than 6% patients: fatigue 5.2%, diarrhea 1.9%, dyspnea 1.3%, dizziness 0.6%, vomiting 0.6%, arthralgia 1.9%, pyrexia 0.6%, and abdominal pain 2.6% (Verstovsek 2012). Hematologic toxicity consisted primarily of anemia and thrombocytopenia. Grade 3/4 anemia occurred in 45.2% patients, Grade 3/4 thrombocytopenia occurred in 12.9% patients, and Grade 3/4 neutropenia occurred less frequently in 7.1% of patients. Approximately half of the Grade 3/4 anemia and thrombocytopenia events occur during the first 8 weeks of therapy. Treatment with INC424 enabled 41.2% to become transfusion independent. Anemia and thrombocytopenia was manageable, and thrombocytopenia generally responded to dose reduction or temporary dosing interruption. Thirteen deaths occurred in the INC424 group vs. 24 deaths in the placebo group (HR, 0.50; 95% confidence interval, 0.25 to 0.98; $P = 0.04$). The rate of discontinuation of the study drug because of AEs was 11.0% in the INC424 group vs. 10.6% in the placebo group.

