11.6.1.1 Full analysis set will be used for all efficacy analyses

The following endpoints are considered in assessing efficacy of INC424 in the study population.

Best overall response to treatment as assessed by spleen palpation, is defined by the investigator.

Change of spleen length from Baseline to end of each visit and at end of treatment. This parameter is computed by dividing the difference of spleen length at assessment time and at baseline by the length at baseline multiplied by one hundred.

WBC and platelet count changes from Baseline at end of each visit and at end of treatment. For each parameter, the percent of change will be computed by dividing the difference of value at assessment time and at baseline by the value at baseline, and multiplying by one hundred.

Shift in fibrosis in the bone marrow from Baseline, is defined as the status change of fibrosis at time of worst/best response (whenever it occur) compared to fibrosis status at baseline. Assessment of fibrosis in the bone marrow after enrollment is not mandatory.

Progression free survival (PFS) is the time from first study drug administration to date of documented progression (based on International Working Group for Myelofibrosis Research and Treatment Response Criteria, IWG-MRT) ([Tefferi A, Barosi G, Mesa RA, et al \(2006\)](#)) or deaths. Time will be censored at the last date the patient is known to be free of disease progression for patients without event.

Leukemia free survival (LFS) is the time from the first study drug administration date to: the date of the bone marrow blast count $\geq 20\%$ OR the date of the first peripheral blood blast count $\geq 20\%$ that is subsequently confirmed to have been sustained for at least 8 weeks or the date of death, whichever occurs first. LFS will be computed whenever data of bone marrow blast and/or peripheral blood blast counts is/are available. Time will be censored at the last date the patient is known to be free of leukemia for patients without event.

Overall survival (OS) is the time from first study drug administration to date of deaths (whatever the cause). Time will be censored at the last date the patient is known to be alive for patients without event.

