$\leq -50\%$, (-50%, -25%], (-25%, -5%], (-5%, 5%], (5%, 25%], (25%, 50%] and $\geq 50\%$

The descriptive summary will include the mean, standard deviation, median, minimum, maximum and 95% CI of the mean over time and at EOT visit for patients who were palpable at baseline and remained palpable or non-palpable at the post-baseline visit considered. In addition, number (n) of patients who remain non palpable, or became palpable from non-palpable at baseline will also be displayed.

WBC and platelet count changes from Baseline at end of each visit/month of therapy and at end of treatment. For each parameter, the percent of change will be computed by dividing the difference of value at assessment time and at baseline by the value at baseline, and multiplying by one hundred. WBC and platelet count changes from baseline will be summarized at end of each visit of therapy and at end of treatment.

Shift in fibrosis in the bone marrow from Baseline, is defined as the status change of fibrosis at time of worst/best response (whenever it occur) compared to fibrosis status at baseline.

Assessment of fibrosis in the bone marrow after enrollment is not mandatory and a listing will be provided with the results of the bone marrow biopsy (if performed).

Progression free survival (PFS) is the time from first study drug administration to date of documented progression (based on International Working Group for Myelofibrosis Research and Treatment Response Criteria) or deaths. Time will be censored at the last date the patient is known to be free of disease progression for patients without event. Deaths on or before the follow up/study completion evaluation visit (on-treatment and post-treatment deaths – Section 3.4.1.2) will be considered in the analyses.

Leukemia free survival (LFS) is the duration from first study drug administration to date of documented leukemia. Observation will be censored, if leukemia is not observed before the

end-of-study, death or lost to follow-up, at last date the patient is known to be free of leukemia. Deaths on or before the follow up/study completion evaluation visit (on-treatment and post-treatment deaths – Section 3.4.1.2) will be considered in the analyses.

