3.11.3 Dynamic International Prognostic Scoring System (DIPSS)

The DIPSS can be used to assess a patient's prognosis as conditions change over time.

The risk level is assigned by the total score:

4 Change to protocol specified analyses

The definitions for the transfusion dependence at baseline, new onset of transfusion dependence and new transfusion independency (protocol v05 section 11.6.4.1) are not current. For the final analysis these definition have been updated as per IWG MRT 2013 ([section 3.6](#) of this SAP).

Clinical Study Report

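### SAP 3.4.3 treats death as a reason to censor LFS, although the protocol counts it as an event; the change is undeclared and the SAP text is ambiguous

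*SAP*

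**What the plan says.** **Protocol 11.6.1.1.** LFS runs from first dose to a marrow blast count of at least 20%, or to a first peripheral blast count of at least 20% "that is subsequently confirmed to have been sustained for at least 8 weeks or the date of death, whichever occurs first". Only patients without an event are censored, at the last date they are known to be leukemia-free.

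**SAP 3.4.3.** LFS "is the duration from first study drug administration to date of documented leukemia". If leukemia is not seen, the patient is censored, and the reasons listed are "end-of-study, death or lost to follow-up, at last date the patient is known to be free of leukemia". The paragraph closes by saying that "Deaths on or before the follow up/study completion evaluation visit" are to be taken into account. It does not say whether they count as events. The same closing sentence follows the PFS and OS definitions. The PFS definition in that section does name death as an event: "Research and Treatment Response Criteria) or deaths".

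**Estimator.** PFS, LFS and OS are all estimated by Kaplan-Meier, with a 95% confidence interval for the median. No competing-risk method is planned.

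**SAP section 4.** One change to the protocol's analyses is declared: "The definitions for the transfusion dependence at baseline, new onset of transfusion dependence and new transfusion independency". LFS is not mentioned.

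**The concern.** A patient who dies without leukemia has an LFS event under the protocol and is a censored observation under the SAP's censoring rule. These are different endpoints with one name. A reader who checks SAP section 4 would conclude that LFS still follows the protocol.

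The closing sentence on deaths can be read in two ways. It may make deaths events, which contradicts the sentence before it. Or it may only fix the period in which deaths are looked at, which leaves the censoring rule in force. Two programmers could therefore produce two different curves from the same data.

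With death censored, Kaplan-Meier treats a competing event as uninformative censoring and estimates time to leukemia. Such a curve cannot be compared with LFS figures that count death. It can also lie above OS. Under the protocol definition every death is also an LFS event, so LFS cannot exceed OS, apart from small differences in censoring dates.

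LFS also has a safety role. Protocol 9.2.1 exempts leukemic transformation, including fatal cases, from SAE reporting because PFS and LFS capture it.

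**Working it through.** **Step 1. The two rules side by side**

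| | Protocol 11.6.1.1 | SAP 3.4.3 |
|---|---|---|
| Event | Leukemia by blast thresholds, "or the date of death, whichever occurs first" | Documented leukemia, no criterion given |
| Death without leukemia | Event on the date of death | Censored at the last leukemia-free date |
| Declared in SAP section 4 | - | No |

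Death triggers censoring in the SAP, but the time used is the last date known free of leukemia, not the date of death.

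**Step 2. Illustration of size**

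Neither document states an LFS figure or an event count, so there is nothing to reproduce. Inputs:

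- Deaths: 13 of 155 on INC424 (8.4%) at a median follow-up of 51 weeks, from the earlier placebo-controlled trial in Protocol 1.3.5. It is borrowed for illustration only.
- Leukemia rate *l*: 0.01, 0.02 and 0.04 per year. These values are assumed; the documents give none.
- Constant, independent hazards (assumed).

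Death hazard: h = -ln(1 - 13/155) / (51/52) = 0.0893 per year.

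24-month OS = exp(-2 × 0.0893) = 83.6%.

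LFS with death as an event = exp(-2(h + l)). With death censored = exp(-2l). Share of protocol events that become censored = h/(h + l).

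| l per year | Death as event | Death censored | Excess (points) | Censored curve above OS (points) | Events lost |
|---|---|---|---|---|---|
| 0.01 | 82.0% | 98.0% | 16.0 | 14.4 | 90% |
| 0.02 | 80.4% | 96.1% | 15.7 | 12.4 | 82% |
| 0.04 | 77.2% | 92.3% | 15.1 | 8.7 | 69% |

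**Step 3. Sensitivity**

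Deaths by 51 weeks of 4% or 15%, and leukemia of 0.5% or 3% per year, all assumed:

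| Deaths by 51 weeks | h | 24-month OS | l | Excess (points) | Above OS (points) |
|---|---|---|---|---|---|
| 4% | 0.0416 | 92.0% | 0.005 | 7.9 | 7.0 |
| 4% | 0.0416 | 92.0% | 0.03 | 7.5 | 2.2 |
| 15% | 0.1657 | 71.8% | 0.005 | 27.9 | 27.2 |
| 15% | 0.1657 | 71.8% | 0.03 | 26.6 | 22.4 |

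**Step 4. The planned median**

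With death as an event and h = 0.0893, the median is ln 2/(h + l) = 7.0, 6.3 and 5.4 years for l = 0.01, 0.02 and 0.04. The longest possible follow-up, from 16 August 2011 to December 2016, is about 5.4 years. With death censored the median is ln 2/l, which is 17.3 years even at l = 0.04. At this death rate the median is therefore unlikely to be reached under either rule, and the difference shows in the curve.

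**The case against.** **The closing sentence may restore the protocol rule.** If death only censors, at the last leukemia-free date, then a window for deaths cannot change any LFS time. The sentence has an effect only if deaths are events, as they are for PFS and OS. This is a fair guide to what the authors may have meant. It does not settle the text, because that reading contradicts the censoring rule immediately before it. The paragraph needs correction on either reading.

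**The gap may be overstated.** The death rate is all-cause, so some of those deaths may have followed leukemia, and adding *l* would count them twice. Under the stated independence the composite formula is exact, but the direction of the point stands. At the opposite extreme, where leukemia is promptly fatal, protocol LFS equals OS. The excess is then the above-OS column: 8.7 to 14.4 points in the main illustration, and as little as 2.2 in the sensitivity range.

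**The borrowed rate may not transfer.** The source trial was 61.2% high-risk. This study also admits intermediate-1 patients and counts deaths only up to the completion visit. This is right, and it is why the figures are only an illustration.

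**LFS carries little weight here.** It is not in a stated secondary objective, the efficacy analyses are called exploratory, nothing is tested, no 24-month percentage is planned, and deaths are reported elsewhere. All of this limits the severity. It does not make the curve correct, and in a descriptive study the curve is the result.

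**Conclusion.** The concern holds. Death is an LFS event in the protocol and a reason for censoring in the SAP. The change is missing from SAP section 4, and the SAP's sentence on deaths leaves their handling open.

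If the censoring rule is programmed, LFS is biased upward against the protocol endpoint. In the illustration the excess at 24 months is 15-16 points, and the curve lies 9-14 points above OS. Over the wider assumed range these figures are 7.5-28 and 2-27 points. They rest on a death rate from another trial, leukemia rates with no source in the documents, and constant, independent hazards.

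The direction does not depend on those numbers: whenever patients die without leukemia, the death-censored curve is the higher one. This should be fixed, but it does not affect the primary safety analysis or any test.

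**What to change.** In SAP 3.4.3, define LFS as the time from first dose to the earlier of two dates: leukemia by the protocol's blast criteria, or death from any cause on or before the follow-up/study completion visit. Delete death from the list of censoring reasons. Restating the blast criteria also closes a smaller gap, since the SAP gives no criterion for documented leukemia.

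If leukemia alone is what the sponsor wants to describe, rename the endpoint *time to leukemia*, estimate it by cumulative incidence with death as a competing event, and declare the change in SAP section 4.

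Either route costs a few lines of SAP text and minor reprogramming of one endpoint. With the first, the reported LFS may look less favourable.
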